**Figure PYAD.6.1. Graphical testing scheme for the primary and key secondary endpoints in Part 1**

For Part 2, the graphical approach shown in [Figure PYAD.6.1](#) will be repeated to compare LY3819253-350mg+LY3832479-700mg versus placebo. If all three endpoints are successful, the testing scheme will then be repeated to compare LY3819253-700mg versus placebo.

All other analyses will be conducted at the two-sided 0.05 significance level without adjustments for multiplicity.

## 6.6. Participant Disposition

The evaluation period disposition and study disposition will be summarized for the Prevention, Treatment, and Safety populations. Disposition summaries will be by treatment group.

Summaries will also include reason for discontinuation from the study tabulated by treatment group.

All patients who are randomized and discontinued from the study will be listed, and the timing of discontinuing (from receiving study treatment) the study will be reported. If known, a reason for their discontinuation will be given.

In addition, a graphical summary (i.e., KM plot) of time from study treatment to early permanent discontinuation of study due to AEs may be generated if there are a substantial number of such events. This graphical summary would be by treatment group and include the log-rank test results.

**Table PYAD.6.4. Tables and Figures Related to Disposition**

Analysis	Details
Patient Disposition	Number and percentage of participants by reason for 
 
study discontinuation and
 
study evaluation period discontinuation
 
 A column that combines all treatment groups (i.e., a total column) will be included (applicable to controlled analysis sets) p-value from Chi-square or Fisher's exact test
Listing of study disposition	--

Analysis	Details
Listing of participants discontinuing due to a decision-related reason (loss to follow-up, patient decision, or investigator decision)	Variables included the reason for study discontinuation, the text collected in the specify field associated with the reasons for discontinuation, and the dates of discontinuation  The text in the specified field should provide information to support that the reason is unrelated to efficacy or safety
Time to early discontinuation of study due to AEs	Presented as a figure (if necessary)

Abbreviation: AE = adverse event.

## 6.7. Participant Characteristics

Patient demographic variables and baseline characteristics will be summarized by treatment and overall for the Prevention, Treatment, and Safety populations. The continuous variables will be summarized using descriptive statistics and the categorical variables will be summarized using frequency counts and percentages. Comparability of baseline covariates across treatment groups will be performed using an analysis of variance (ANOVA). By-patient listings of basic demographic characteristics (i.e., age, sex, race, racial subgroup, ethnicity, and body weight) for the Enrolled/ITT population will be provided.

Within each population, demographic variables and baseline characteristics will be summarized by treatment group and overall for each role within the facility (residents and staff). No comparisons across treatment groups will be made within these subgroups.

**Table PYAD.6.5. Tables and Figures Related to Demographics and Other Characteristics of Study Population**

Analysis	Details
Baseline Demographic Characteristics	
Variables to be included:
 
 
• Age
 
• Sex
 
• Race (Amerian Indian or Alaska Native, Asian, Black or African American, Native Hawaiian or Other Pacific Islander, White, Multiple), and
 
• Ethnicity (Hispanic or Latino, Not Hispanic or Latino, Not Reported)
 
• Height
 
• Weight
 
 
Statistics to be included:
 
Continuous: Mean, standard deviation, min, max, median, and 10th and 90th percentiles
 
Categorical: n and percent (denominator for percentages will be the number of participants with nonmissing values) A column that combines all treatment groups (i.e., a total column) will be included (applicable to controlled analysis sets) No inferential statistics

Medical History and Preexisting conditions	
Number and percentage of participants with medical history events and preexisting conditions using MedDRA PT nested within SOC
 
 
• Ordered by decreasing frequency within SOC on the LY arm
 

Analysis	Details
	Preexisting conditions are defined as those conditions with a start date prior to the first dose of the study drug and stop dates that are at or after the informed consent date or have no stop date (i.e., are ongoing).
Listing demographics	--

Abbreviations: max = maximum; MedDRA = Medical Dictionary for Regulatory Activities; min = minimum; PT = preferred term; SOC = System Organ Class.

## 6.8. Treatment Compliance

Participants will receive study intervention directly from the investigator or qualified designee, under medical supervision. The date and time of dosing will be recorded in the source documents and recorded in the CRF. Treatment compliance will not be reported.

## 6.9. Prior Medication and Concomitant Therapy

Medications will be classified into anatomical therapeutic chemical (ATC) drug classes using the latest version of the WHO drug dictionary. Medication start and stop dates will be compared to the date of the first dose of treatment to allow medications to be classified as concomitant.

*Prior medications* are those medications that start and stop prior to the date of the first dose of study treatment. *Concomitant medications* are those medications that start before, on, or after the first day of study treatment and continue into the evaluation period. For all summary tables of concomitant medications, Preferred Terms of concomitant medication will be sorted by descending frequency in the LY arm.

**Table PYAD.6.6. Summary Tables Related to Concomitant Medications**

Analysis	Details
Prior medications	Number and percentage of participants using Preferred Terms of prior medication 
 
Ordered by decreasing frequency
 
 p-value from Chi-square or Fisher's exact test.
Concomitant medications	Number and percentage of participants using Preferred Terms of concomitant medication 
 
Ordered by decreasing frequency
 
 p-value from Chi-square or Fisher's exact test

## 6.10. Efficacy Analyses

### 6.10.1. Primary Outcome and Methodology

The endpoint for the primary analysis is defined as the first occurrence of COVID-19, defined as the detection of SARS-CoV-2 by reverse transcription – polymerase chain reaction (RT-PCR) AND mild or worse disease severity within 21 days of detection, by Day 57 (8 weeks after randomization).

The percentage of patients in the Prevention population who experience COVID-19 by Day 57 will be summarized by treatment group.

Statistical comparison between each study intervention and placebo will be done using a logistic regression model. The model will include treatment, facility, role within the facility (resident vs staff) and sex as fixed effects. The odds ratio and the corresponding CIs, as well as the treatment differences and the corresponding CIs, will be computed using the Wald method and reported. A p-value from the Rao's score test will be reported.

As an exploratory analysis, the incidence of COVID-19 within 21 days of randomization will be compared across treatment groups in the subset of participants in the Treatment population who are asymptomatic at baseline (as defined in Table 1 of the protocol). Statistical comparisons will use similar methodology as described in Section 6.10.1.

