9.2. Sample Size Determination

For Part 1, an estimated 33 events are needed to show superiority of LY3819253 4200 mg over placebo in each of the primary and key secondary endpoints, using the formula by Schoenfeld (1983). An average sample size of approximately 1300 participants who are SARS-CoV-2 PCR negative and serology negative at baseline is expected to obtain the needed number of events for each endpoint.

For Part 2, an estimated 56 events in the Prevention Cohort are needed to show superiority over placebo for either LY3819253 700 mg or LY3819253 350 mg+LY3832479 700 mg in each of the primary and key secondary endpoints. Approximately 2000 participants on average will be randomly assigned to study intervention such that approximately 1700 participants are randomized in the Prevention Cohort with the goal of achieving approximately 56 events on each of the primary and key secondary endpoints.

Due to the dynamic nature of the pandemic, Part 3 will enroll at least 30 participants and up to approximately 500 participants randomized to either LY3819253 700 mg or LY3819253 700 mg + LY3832479 1400 mg. Part 3 of the study is considered exploratory and is not powered for inference between the two treatment arms.

The maximum sample size for this study is approximately 5000 participants in the intent-to-treat (ITT) population.

Participants will be residents and staff of skilled nursing and assisted living facilities. Globally, there are many reports of the rapid spread of COVID-19 amongst residents of skilled nursing facilities following identification of an index case, with high associated rates of morbidity and mortality (Arons et al. 2020; Grabowski). Given that residents at these facilities are at higher risk for having a more severe disease course of COVID-19, this will be an important population to participate in the study. Therefore, a minimum of 300 residents will be enrolled.

Operationally, this will be accomplished, when possible, by identifying facilities where approximately half of the participants interested in the study are residents.

For sample size determination for Part 1, the following assumptions were used:

- 1) two-sided significance level of 0.05;
- 2) 90% power for the primary and key secondary endpoints;
- 3) an 8-week placebo group event rate of 4.0% for moderate or worse severity COVID-19;

4) a risk ratio of 0.33 between LY3819253 and placebo in terms of the primary and key secondary endpoints.

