Treatment comparisons of continuous efficacy and safety variables with a single postbaseline timepoint will be made using analysis of covariance (ANCOVA) with: (a) treatment group, (b) facility, (c) role within the facility (resident vs staff), (d) sex and (e) baseline value in the model. Type III sums of squares for LS means will be used for statistical comparison between treatment groups. The LS mean difference, standard error, p-value-, and 95% CI, unless otherwise specified, will also be reported. Missing data imputation method for the ANCOVA model is specified in Section 6.3.

Treatment comparisons for binary efficacy endpoints will be made using logistic regression. The model will include the treatment groups, facility, and the stratification factors (resident/staff and sex) as explanatory variables. For the primary and key secondary endpoints, p-values from Rao's score test (or score test) will be reported (Rao 1948). For all other endpoints, results from a Wald test will be reported. The odds ratio and the corresponding CIs, as well as the treatment differences and the corresponding CIs, will be reported.

For other binary endpoints, treatment comparisons will be made using Chi-square tests if the expected count is at least 5 in at least 80% of the cells, otherwise a Fisher's exact Test will be used.

The Kaplan-Meier (KM) product limit method will be used for time-to-event analyses. The hazard ratio and log-rank test will be reported. Time for all analyses will be described in units of days.

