### ***6.10.2. Additional Analyses of the Primary Outcome***

#### **6.10.2.1. Random Effect for Facility**

As a sensitivity assessment, the primary outcome will be assessed using a generalized linear mixed model (GLMM). The model will include treatment and the randomization stratification factors as fixed effects and facility as a random effect.

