### ***6.10.3. Secondary Efficacy Analyses***

#### **6.10.3.1. Incidence of Moderate-or-Worse Severity COVID-19 by Day 57**

As a key secondary endpoint, the proportion of patients in the Prevention populations who develop moderate-or-worse severity COVID-19 (defined as the detection of SARS-CoV-2 by polymerase chain reaction (RT-PCR) AND moderate or worse disease severity within 21 days of detection) by Day 57 will be summarized by treatment group. Similar methodology, as described in Section 6.10.1 will be utilized for statistical hypothesis testing, following the testing scheme described in Section 6.5.

As a sensitivity assessment, participants who develop COVID-19 within 21 days of becoming SARS-CoV-2 positive by RT-PCR, then continue on to develop moderate-or-worse disease severity by Day 57, will be included as moderate-or-worse severity COVID-19 events in the assessment.

As an exploratory analysis, the incidence of moderate-or-worse severity COVID-19 within 21 days of randomization will be compared across treatment groups in the subset of participants in the Treatment populations who did not have moderate-or-worse severity COVID-19 at baseline. Statistical comparisons will use similar methodology as described in Section 6.10.1.

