#### **6.10.3.2. Incidence of SARS-CoV-2 Infection by Day 29**

As a key secondary endpoint, the proportion of patients in the Prevention populations who are SARS-CoV-2 positive postbaseline (Table PYAD.4.1) by Day 29 will be summarized by treatment group. Similar methodology, as described in Section 6.10.1 will be utilized for statistical hypothesis testing, following the testing scheme described in Section 6.5.

Results of SARS-CoV-2 tests during the study will be listed for each participant.

As a sensitivity analysis, the percentage of patients in the Prevention population who experience death or are SARS-CoV-2 positive postbaseline by Day 29 will be summarized by treatment group. Similar methodology, as described in Section 6.10.1 will be utilized for statistical hypothesis testing.

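### Fixed facility intercepts in the primary and key secondary logistic models make the score test mildly anti-conservative and exaggerate the odds ratio if facilities are small; facility size is not stated

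*SAP*

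**What the plan says.** SAP 6.10.1 defines the primary test: "The model will include treatment, facility, role within the facility (resident vs staff) and sex as fixed effects". The p-value comes from Rao's score test; the odds ratio, the treatment difference and their intervals use the Wald method. SAP 6.1.4 gives the same model for binary efficacy endpoints in general: "The model will include the treatment groups, facility, and the stratification factors (resident/staff and sex) as explanatory variables". It adds: "For the primary and key secondary endpoints, p-values from Rao's score test (or score test) will be reported".

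SAP 6.10.3.1 carries the model to moderate-or-worse COVID-19: "Similar methodology, as described in Section 6.10.1 will be utilized for statistical hypothesis testing, following the testing scheme described in Section 6.5". SAP 6.10.3.2 does the same for infection by Day 29. SAP 6.5 tests the primary endpoint at 0.05, then infection at 0.01 and moderate-or-worse disease at 0.04, with 0.05 available to either once the other succeeds.

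The one alternative handling of facility within a logistic model is SAP 6.10.2.1: "The model will include treatment and the randomization stratification factors as fixed effects and facility as a random effect". It covers the primary outcome only. Neither document provides for conditional or penalized likelihood, for pooling small facilities, or for an expected number or size of facilities. Protocol 9.2 plans Part 1 around about 1300 participants, where "an estimated 33 events are needed to show superiority".

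**The concern.** Facility intercepts are nuisance parameters whose number grows with recruitment. Unconditional maximum likelihood estimates each one from that facility's participants alone. When these are few, the model variance of the treatment score is too small and the treatment coefficient is biased away from zero. Both errors favour the active arm.

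At stake are the confirmatory p-values for the primary and key secondary endpoints and the reported odds ratios. The key secondary endpoints are more exposed because none of their planned sensitivity analyses changes how facility is handled. Those analyses change the event definition, the population (Fully Dosed) or the weights.

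**Working it through.** **Inputs from the documents.** Protocol 9.2 and SAP 5.2 (Part 1): about 1300 participants, 33 events, two-sided 0.05, 90% power, placebo rate 4.0% for moderate-or-worse disease, risk ratio 0.33. Protocol 6.3: 1:1 allocation, blocked within facility and stratified by role and sex.

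**Inputs assumed.** 20 to 150 facilities, with 260 as an extreme; skewed facility sizes; facility log-odds SD of 1; blocks of 4; an assumed role and sex mix.

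**1. The plan's own figure.** Rates of 4.0% and 0.33 × 4.0% = 1.32% give an odds ratio of (0.0132/0.9868)/(0.04/0.96) = 0.321. Schoenfeld's formula gives 4 × (1.960 + 1.282)²/(ln 0.321)² ≈ 42.03/1.291 = 32.6, so 33 events, as stated. Expected events in 1300 are 650 × 0.04 + 650 × 0.0132 = 34.6. The target is reproduced.

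**2. Why the score test is too large.** Take a facility with m participants, t of them treated, and d events. Both tests use the same score, the sum of (treated events − d·t/m). The variances differ:

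- Unconditional model: sum of d(m−d)t(m−t)/m³
- Conditional (hypergeometric): sum of d(m−d)t(m−t)/[m²(m−1)]

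With equal facility sizes the second is m/(m−1) times the first, so the unconditional chi-square is m/(m−1) times the facility-stratified Cochran-Mantel-Haenszel (CMH) chi-square. Events enter both through the same factor d(m−d) and cancel. Facilities without events contribute nothing to either. The implied type I error at nominal 5% is P(χ²₁ > 3.84 × (m−1)/m).

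**3. Simulation of the SAP model.** The model had facility intercepts, role and sex, with a Rao score test. There were 12,000 null and 4,000 alternative trials per setting, with a Monte Carlo standard error of about 0.2 points on type I error. The placebo rate was 4% and the true odds ratio 0.321. The comparators were the CMH test and the Mantel-Haenszel (MH) odds ratio.

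| Facilities (participants each) | m/(m−1) formula | Type I, SAP model | Type I, CMH | SAP model at nominal 1% | Median OR, SAP model | Median OR, MH | Excess in log OR |
|---|---|---|---|---|---|---|---|
| 20 (65) | 5.2% | 5.0% | 4.8% | 0.95% | 0.302 | 0.312 | 3% |
| 50 (26) | 5.5% | 5.7% | 4.9% | 1.1% | 0.298 | 0.315 | 5% |
| 75 (17) | 5.7% | 5.7% | 4.7% | 1.1% | 0.295 | 0.320 | 7% |
| 100 (13) | 6.0% | 6.2% | 5.1% | 1.4% | 0.292 | 0.320 | 8% |
| 150 (8.7) | 6.5% | 6.0% | 4.6% | 1.3% | 0.275 | 0.317 | 12% |
| 260 (5) | 8.0% | 7.4% | 5.3% | 1.9% | 0.256 | 0.321 | 20% |

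The last column is the ratio of the two log median odds ratios, minus 1. For example, at 150 facilities ln 0.275/ln 0.317 = 1.291/1.149 = 1.12. At nominal 4%, the SAP model gave 4.0% to 5.0% for 20 to 150 facilities and 6.2% at 260.

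**4. What drives it.** At 75 facilities, 0.35, 0.69 and 2.6 events per facility gave 5.5%, 5.7% and 5.7%. At 20 facilities, 0.85 and 9.7 events per facility gave 5.4% and 5.2%. Type I error barely moves with events per facility; it follows participants per facility. At 75 facilities, a facility SD of 1.5 or blocks of 2 gave 5.6%.

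Transmission between participants within a facility was not modelled, and the random-facility model was not fitted.

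**The case against.** The strongest objection is that the decisive input is missing and the effect is small over most plausible values. Residents and staff are both recruited and randomization is blocked within facility, so very small facilities cannot be presumed. At 13 per facility, the factor 13/12 turns a reported p of 0.05 into about 0.06, so only borderline results change. The odds-ratio shift there, ln(0.321/0.292) ≈ 0.09, is under a quarter of a standard error: 33 events split about 25/8 give √(1/25 + 1/8) ≈ 0.41. All of this stands, and it limits the severity.

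The plan also has checks for the primary outcome: the random-facility model, and in SAP 6.10.2.2 an unadjusted risk difference and a Cox hazard ratio with no facility term specified. For hospitalization and death, logistic regression is run only if the data suffice. These points stand too, but the checks on the primary outcome do not reach the key secondary endpoints or change the confirmatory p-value.

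Adjusting for facility is right in itself: Protocol 9.4.5 calls for it and the randomization is blocked on it. The issue is only how the adjustment is done.

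A reader might infer that having more facilities than events, or many facilities with none, is what breaks the test. Steps 2 and 4 show otherwise. A reader might also infer that the 0.05 level is violated. The documents cannot support that without facility sizes; with 20 facilities of 65 the simulated level is 5.0%.

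**Conclusion.** The point holds in conditional form. The direction is certain: the planned score test is never more conservative than its facility-conditional counterpart, and the odds ratio is biased in the drug's favour. The size depends on participants per facility. It runs from nil to about 1 percentage point of type I error, and about 3% to 12% on the log odds ratio, for 20 to 150 facilities in Part 1. It becomes clearly material at about 5 or 6 per facility (about 7% and 20%). These figures rest on the assumptions listed in the working and were derived for Part 1. Part 2 uses the same model, but its size was not computed.

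The same method is reused for exploratory analyses in the Part 1 Treatment population. That is at most about 1700 − 1300 = 400 people, so strata there would be smaller.

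The stated levels are not assured, and a cheap remedy exists. Severity is moderate; the figures do not support calling the confirmatory analysis invalid.

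**What to change.** - In SAP 6.10.1 and 6.1.4, take the score p-value, odds ratio and confidence interval for the primary and both key secondary endpoints from conditional logistic regression stratified on facility, with treatment, role and sex as covariates.
- Conditional likelihood removes the facility intercepts, so it cannot supply the treatment differences that 6.10.1 also requires. Report these from the unadjusted risk difference already in 6.10.2.2 (extended to the key secondary endpoints) or from a facility-stratified Mantel-Haenszel risk difference.
- Extend the random-facility sensitivity analysis in 6.10.2.1 to both key secondary endpoints.
- State the expected number and size of facilities.

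The cost is SAP wording, minor programming and a slightly larger p-value. With the stratified CMH test standing in for the conditional model, a simulation showed a power loss of about 1 percentage point or less. In the simulations above, facility-stratified inference held type I error at 4.6% to 5.3% and gave median odds ratios of 0.312 to 0.321 against a true 0.321. The change should be made before the part concerned is unblinded.

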### ***6.10.2. Additional Analyses of the Primary Outcome***

#### **6.10.2.1. Random Effect for Facility**

As a sensitivity assessment, the primary outcome will be assessed using a generalized linear mixed model (GLMM). The model will include treatment and the randomization stratification factors as fixed effects and facility as a random effect.

#### **6.10.2.2. Risk Difference/Time-to-Event Assessment**

The risk difference for COVID-19 between treatments will be estimated by the difference in the percentages of patients in the Prevention population who experience COVID-19 by Day 57, unadjusted for other covariates. A Wald 95% confidence interval for the risk difference will be computed.

The time from randomization to first incidence of COVID-19 will be summarized by treatment for participants within the Prevention population. A 95% confidence interval for the hazard ratio will be computed using a Cox proportional hazards model. Participants who have yet to complete the Evaluation Period at the time of the analysis will be censored at the date of their last visit prior to the analysis.

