## **5.2. Determination of Sample Size**

For Part 1, an estimated 33 events are needed to show superiority of LY3819253-4200mg over placebo in each of the primary and key secondary endpoints, using the formula by Schoenfeld (1983). An average sample size of approximately 1300 participants who are SARS-CoV-2 PCR negative and serology negative at baseline is expected to obtain the needed number of events for each endpoint.

For Part 2, an estimated 56 events in the Prevention Cohort are needed to show superiority over placebo for either LY3819253-700mg or LY3819253-350mg+LY3832479-700mg in each of the primary and key secondary endpoints. Approximately 2000 participants on average will be randomly assigned to study intervention such that approximately 1700 participants are randomized in the Prevention Cohort with the goal of achieving approximately 56 events on each of the primary and key secondary endpoints.

The maximum sample size for this study is approximately 5000 participants in the intent-to-treat (ITT) population.

Participants will be residents and staff of skilled nursing and assisted living facilities. Globally, there are many reports of the rapid spread of COVID-19 amongst residents of skilled nursing facilities following identification of an index case, with high associated rates of morbidity and mortality (Arons et al. 2020; Grabowski). Given that residents at these facilities are at higher risk for having a more severe disease course of COVID-19, this will be an important population to participate in the study. Therefore, a minimum of 300 residents will be enrolled.

Operationally, this will be accomplished, when possible, by identifying facilities where approximately half of the participants interested in the study are residents.

For sample size determination for Part 1, the following assumptions were used:

- 1) two-sided significance level of 0.05;
- 2) 90% power for the primary and key secondary endpoints;
- 3) an 8-week placebo group event rate of 4.0% for moderate or worse severity COVID-19;
- 4) a risk ratio of 0.33 between LY3819253 and placebo in terms of the primary and key secondary endpoints.

For sample size determination for Part 2, the following assumptions were used:

- 1) two-sided significance level of 0.025;
- 2) 90% power for the primary and key secondary endpoints;
- 3) an 8-week placebo group event rate of 5.3% for moderate or worse severity COVID-19;

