### **6.1.5. Timing of Primary Analysis**

#### **6.1.5.1. Part 1 Primary Analysis**

To ensure that all primary and key secondary endpoints are well-powered, database lock for the primary and key secondary endpoints in Part 1 (the Part 1 Primary Database Lock) will be triggered when at least 300 facility residents have been enrolled and when 33 participants in the Part 1 Prevention population experience a moderate or worse severity case of COVID-19. All pre-specified analyses will be based on the Primary Database Lock. However, if the accumulation of moderate or worse severity cases of COVID-19 occurs slower than expected, the Primary Database Lock may be triggered when at least 36 participants in the Part 1 Prevention population test positive for SARS-CoV-2 within 4 weeks of randomization. If this is the case, only the primary endpoint will be evaluated at the Primary Database Lock. At the time of the primary analysis for Part 1, only data from patients enrolled in Part 1 will be unblinded to the sponsor.

To account for participants who have not finished the Evaluation Period at the time of the Primary Database Lock, a supplementary database lock (the Part 1 End of Evaluation Database Lock) will occur once all participants have completed the Evaluation Period or discontinued from the study. The analyses conducted during the Primary Database Lock will be re-evaluated at the End of Evaluation Database Lock.

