### ***6.3.2. Missing COVID-19 Status or Disease Severity***

For the primary and key secondary endpoints, if a participant has at least one post-baseline RT-PCR test result and has not yet met the criterial for COVID-19 or is missing data used to determine COVID-19 status, the participant will be treated as not experiencing COVID-19. The same logic will be used for moderate-or-worse severity COVID-19.

As a supplementary analysis on these endpoints, the approach described in Section [6.3.1](#) will be used to handle missing COVID-19 status or disease severity due to death unrelated to COVID-19, study discontinuation, or the triggering of the Primary Database Lock. Participants with missing information will be treated as not experiencing the associated endpoint event and will be weighted based on the proportion of the Evaluation Period that was completed.

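### At the event-driven Primary Database Lock, the Day 57 percentages and the crude risk difference count participants with incomplete follow-up as full 8-week non-events

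*SAP*

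**What the plan says.** - **When the data are cut.** Part 1 enrols until the required events and the minimum number of residents are reached (Protocol 1.1, Intervention Groups and Duration). The lock is triggered by 33 moderate-or-worse cases plus at least 300 residents in Part 1, with a fallback trigger of 36 infections within 4 weeks, and by 56 moderate-or-worse cases in Part 2 (SAP 6.1.5.1, 6.1.5.2). For Part 1, "All pre-specified analyses will be based on the Primary Database Lock"; SAP 6.1.5.2 has an equivalent sentence for Part 2.
- **How incomplete follow-up is scored.** Participants with no post-baseline RT-PCR result are excluded (SAP 6.3.1). A participant with at least one result who "has not yet met the criterial for COVID-19" is treated as not having the event (SAP 6.3.2).
- **What is reported.** Arm percentages by Day 57 (SAP 6.10.1, 6.10.3.1) and a risk difference "estimated by the difference in the percentages of patients in the Prevention population who experience COVID-19 by Day 57, unadjusted for other covariates", with a Wald interval (SAP 6.10.2.2).
- **The hazard ratio, in the same section.** "Participants who have yet to complete the Evaluation Period at the time of the analysis will be censored at the date of their last visit".
- **Safeguards.** A supplementary logistic regression weights participants by the share of the Evaluation Period completed and expressly covers truncation by the lock (SAP 6.3.1, 6.3.2). An End of Evaluation Database Lock repeats the analyses once everyone has completed or discontinued (SAP 6.1.5.1, 6.1.5.2).

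**The concern.** A percentage labelled as incidence by Day 57 should describe 8 weeks at risk. At an event-driven cut with enrolment still open, a participant followed for 10 days without an event enters the denominator exactly like one followed for 57 days. The percentage then averages risk over whatever follow-up has accrued, and the risk difference inherits this. One section of the SAP treats the same people as event-free for one estimate and as censored for the next, so the two cannot be read together.

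At stake are the absolute figures at the first readout: the incidence in each arm, the risk difference and any number needed to treat derived from it. The confirmatory test is not at issue.

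**Working it through.** **Inputs.** From SAP 5.2: "two-sided significance level of 0.05"; "90% power for the primary and key secondary endpoints"; "an 8-week placebo group event rate of 4.0% for moderate or worse severity COVID-19"; "a risk ratio of 0.33 between LY3819253 and placebo in terms of the primary and key secondary endpoints". Allocation is 1:1 (Protocol 6.3), with about 1300 participants in the Part 1 Prevention population. No placebo rate is given for the primary (mild-or-worse) endpoint, so percentage points below are illustrative for it. Accrual duration is not given and is assumed.

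**Step 1: the plan's event count.** Schoenfeld, 1:1: events = 4(1.960 + 1.282)² / (ln HR)².
- HR 0.33: 34.2.
- Risk ratio converted to a hazard ratio, ln(1 − 0.0132)/ln(1 − 0.04) = 0.3255: 33.4.

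The stated 33 reproduces.

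**Step 2: fully followed target.** Active rate 0.33 × 4.0% = 1.32%. Risk difference 4.00 − 1.32 = 2.68 points.

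**Step 3: shortfall on the plan's own N and events.** Full follow-up of 1300 gives 650 × (0.040 + 0.0132) = 34.6 events. A lock at 33 has seen 33/34.6 = 95% of them, so the crude risk difference is about 2.68 × 0.954 = 2.56, a 5% shortfall.

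**Step 4: shortfall under assumed accrual.** Assume uniform accrual over A weeks, a lock at the end of accrual, and exclusion of those under 1 week as a stand-in for having no post-baseline swab. With a near-constant hazard, the observed fraction of 8-week risk is about [∫₁⁸ (t/8)dt + (A − 8)]/(A − 1) = [3.94 + A − 8]/(A − 1). For A = 12 this is 7.94/11 = 0.72. The table uses the exact exponential form. The last column instead puts 70% of events in weeks 1 to 4.

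| Accrual (weeks) | Incomplete | Placebo % | Active % | RD, constant hazard (share of 2.68) | RD, front-loaded |
|---|---|---|---|---|---|
| 8 | 100% | 2.26 | 0.74 | 1.52 (57%) | 1.80 |
| 12 | 64% | 2.90 | 0.95 | 1.94 (72%) | 2.12 |
| 16 | 47% | 3.19 | 1.05 | 2.14 (80%) | 2.27 |
| 20 | 37% | 3.36 | 1.11 | 2.25 (84%) | 2.36 |
| 26 | 28% | 3.51 | 1.16 | 2.36 (88%) | 2.43 |

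The range is about 1.5 to 2.4 points, a 9% to 43% shortfall. (Differences are taken before rounding.)

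**Step 5: are those scenarios compatible with the plan?** At planned rates, 33 events need 33/0.0266 = 1241 fully followed participants, so a fraction f needs 1241/f: about 1,410 at 88% and 2,180 at 57%. The larger shortfalls therefore imply more enrolment than the planned average of 1300, or a higher event rate.

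**Step 6: relative effect.** In the same scenarios the crude odds ratio is 0.322 to 0.324, against 0.321 fully followed.

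**Step 7: does the planned weighting repair the percentages?** If it were applied to them, the risk difference would be 2.66 to 2.68 under constant hazard, but 2.76 to 3.14 when events are front-loaded.

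**Step 8: direction.** The lock risk difference averages RD(t) over the achieved follow-up times. It can exceed the 8-week value only if RD(t) is higher earlier, which requires active-arm events to outpace placebo events late. With 85% of placebo events in the first 3 weeks and nearly all active-arm events in weeks 7 and 8, it is 2.85 to 3.05 (accrual 8 to 16 weeks). With the same late active-arm events but evenly spread placebo events, it is still below target, at 2.01 to 2.37.

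**The case against.** The truncation was foreseen. The risk difference is recomputed at the End of Evaluation lock in both parts, a follow-up-weighted regression is planned, and the Cox model censors properly. Truncation is balanced by randomization, so the treatment comparison is sound. On the plan's own numbers the shortfall is 5%; the larger figures rest on assumed accrual. A plain Kaplan-Meier remedy has its own flaw: in nursing-home residents, death from other causes is a competing event, and censoring it overstates cumulative incidence.

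Most of this stands and limits the point. It does not remove it. The weighting applies to the logistic regression, not to the reported percentages or the risk difference, and it overshoots if events cluster early, which is plausible when enrolment follows an index case. The second lock is called supplementary, and the SAP does not say which lock supplies the headline absolute figures. Discontinued participants with a swab still count as event-free there. The 5% figure needs N near 1300 at the lock, which SAP 5.2 describes as an average.

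A reader might go further and infer that the trial's 8-week figures are simply understated. The documents do not support that, because the analyses are repeated after full follow-up. Nor do they support inferring, from the half-life of about 19 days, that waning makes the lock overstate the relative effect. Protocol 4.3 chose the Part 1 dose to keep concentrations above the neutralization target in 90% of participants for at least 8 weeks, and no week-specific hazard ratios are given.

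**Conclusion.** The point holds for the absolute figures at the Primary Database Lock. Incidence there is biased low in both arms. The risk difference is also biased low unless the effect reverses late in the window. The shortfall is about 5% (2.56 against 2.68 points) on the planned N and events, and 9% to 43% under uniform accrual over 8 to 26 weeks. These sizes rest on assumed accrual and event timing and on a rate for moderate-or-worse disease. The mechanism rests only on the SAP text. Under a stable relative effect the odds ratio and the confirmatory test are almost unaffected. Part 2 has the same structure; its size was not computed. The change is worth making because it replaces a stated estimator that does not estimate what its label says.

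**What to change.** In SAP 6.10.1, 6.10.2.2 and 6.10.3.1:

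1. At the Primary lock, estimate the Day 57 risk in each arm and the risk difference with a time-to-event estimator that uses the censoring rule already written for the hazard ratio. Either use Kaplan-Meier with a Greenwood-based interval, or Aalen-Johansen cumulative incidence with death unrelated to COVID-19 as a competing event. State which, and how such deaths are handled.
2. Name the End of Evaluation lock as the source of the headline absolute 8-week incidence and risk difference. Use the same estimator there, so that participants who discontinue are censored rather than counted as event-free.
3. Leave the confirmatory test at the Primary lock unchanged.

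The cost is SAP wording, since Kaplan-Meier and Cox methods are already planned, and slightly wider intervals at the Primary lock. Design, alpha and conduct do not change.
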